5 STUDY TIMELINES

5.1 Duration of an Individual Subject's Participation in the Study

The proposed study consists of multiple videoconferencing sessions (a total of 3) throughout a 2-week field study. Following informed consent, participants will be randomly assigned to 1 of 4 message conditions and use the assigned product for 2 weeks. This 2-week field study involves participants logging their use of tobacco products, while the weekly videoconferencing sessions involve additional questionnaires and guidance about field data collection.

Roswell Park Protocol Number: I 757820

	Data Collection Sessions (Weekly)			Field (Daily for 14 days)
	Video 1	Video 2	Video 3	Ecological Momentary Assessment
Tobacco Use Behavior				
Cigarettes per Day	X	X	X	X
Other Tobacco Use	X	X	X	X
Context of Use (e.g., location)				X
Questionnaires				
Message Perceptions (response, health risk, purchase)	X All messages	X Randomly Assigned Message	X Randomly Assigned Message	
Vent Awareness	X	X	X	
Product Evaluation (Duke Sensory, Product Evaluation Scale, Drug Effects, Hedonic Attribute)	X	X	X	X Select Items
Readiness to Quit (Contemplation Ladder)	X	X	X	
Withdrawal (MNWS, QSU-B, PANAS)				X Select Items
Attention to Messaging				X
Biomarkers				
Exhaled CO				X
Topography via Filter Analysis				X

Estimated date for the investigators to complete this study

Data collection should be completed by 12/31/2022.

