In the event of REDCap being inaccessible for a study visit, .pdf files or paper copies of the consent will be provided to the participants and the participants will be able to sign and return or submit a photo of the signed copy.

The participant will then be randomized to 1 of 4 message conditions (No message, Neutral message, Compensation message, Blocking message) and arrangements will be made to mail, deliver, or have participants pick up study materials (study cigarettes with pack messages, CO

Roswell Park Protocol Number: I 757820

monitor, scales, butt collection materials, shipping materials, etc.). Participants will be provided with two weeks of materials.

Session 1. Session 1 will occur upon receipt of study materials by the participant. Participants will complete a baseline intake questionnaire including smoking and tobacco use history, nicotine dependence scales, SCQ, TRIRISK, delay discounting, respiratory symptoms, and knowledge, attitudes, and beliefs about filter vents. In addition, participants complete questionnaires on message perceptions (response to messaging, health risk, purchase intention) for all pack messages. Questionnaires also will be used to get baseline assessments of the user's usual brand of cigarettes (Duke Sensory Scale, Product Evaluation Scale, Hedonic Attribute Scale). Participants will be instructed to record each smoking event using the EMA app provided (described in more detail below) and to retain all spent cigarette butts and unused product. Participants will be informed that they are free to use other tobacco products (though they will not be provided as part of the study), and that these should be recorded using EMA. Participants will be provided for cigarettes for a total of two weeks, with the amount determined by normal self-reported weekly consumption rounded to nearest whole pack.

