Remote Data Collection. Participants will complete the two-week study remotely using EMA methods. At the conclusion of Session 1, participants will be trained to record their assigned product use via EMA for data collection. Specifically, participants will respond to 5 scheduled questionnaires daily. These questionnaires are designed to assess product consumption, context of use (e.g., location, social situation), and subjective responses (e.g., withdrawal, product evaluation, message attention - more details on surveys provided below). Participants will be prompted to measure their exhaled-air CO level and product weight twice each day using a personal monitor provided to them. Participants will also retain all spent cigarette butts and unused products throughout the two weeks.

Day 3 Check-in: Research assistants will monitor EMA data to ensure the participant is compliant with study procedures. Participants will send a secure text message (via Twilio) or arrange a phone call to discuss the participant's compliance in the initial days of data collection. Participants that are not responding to prompts will be retrained to ensure they understand procedures and warned that compliance must increase to continue participating in the study.

Session 2 will take place one week later (\pm 2 days) via remote videoconference using an institution-approved software with a password protected meeting (e.g., WebEx, Microsoft Teams, Zoom). The Session 2 videoconference will include the completion of questionnaires on vent awareness, product evaluation, and readiness to quit (similar to Visit 1). Participants will again be asked on message perceptions, but only in relation to their randomly assigned condition.

Session 3 will take place one week later (\pm 2 days) via remote videoconference. The same questionnaires from Session 2 will be administered again. Laboratory staff will guide participants to place all materials (retained filter butts, unused products, unsigned payment receipts) in the provided shipping box. Arrangements will be made for the participant to return materials or for research staff to pick up materials. Participants will be paid for Visit 3 upon verification of returned study materials.

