11.4 Data To Be Collected

- **Baseline measures and covariates will assess:**
 - Demographics (age, sex, race/ethnicity, education, income)

Roswell Park Protocol Number: I 757820

- Tobacco use behaviors (consumption, brand, menthol preference, past quit attempts)
- Delay discounting
- A series of previously used items will assess knowledge and perceptions of filter vents.^{113,117}
- Nicotine dependence will be assessed using:
 - Fagerström Test for Nicotine Dependence (FTND¹¹⁸)
 - PROMIS

Behavioral aspects of cigarette dependence will be assessed using:

- The Glover-Nilsson scale^{120,121}
- The different scales are used to capture different dimensions of tobacco dependence.¹²²
- Exhaled air CO will be collected by the participants twice each day using a personal CO monitor provided by the researchers. The CO monitors provided are coVita iCo™ Smokerlyzers®, which are intended for research and consumer use and are compatible with a Smartphone or tablet (iOS or Android).

Perceptions of product messaging: In this study, we are interested in risk perceptions, smoking-related expectancies, and behavioral intentions. We will assess risk perceptions for specific products using a risk ladder.¹²⁹ More generalized perceptions of risk for cancer are captured using the tripartite risk (TRIRISK) measure, which captures deliberative, affective, and experiential components of risk perception.¹³⁰ The adult smoking consequences questionnaire (SCQ) will assess smoking-related expectancies.^{103,131} Behavioral intention is assessed using Juster's consumer purchase probability scale, a widely used marketing metric.¹³²⁻¹³⁴ Additional questions will include responses to messaging (e.g., message was powerful, memorable).

Responses to product use will be assessed in a number of ways: Response to nicotine dose will be assessed using the Minnesota Nicotine Withdrawal Scale (symptoms of nicotine withdrawal).¹³⁵ Cigarette craving in field will be assessed using the Brief QSU commonly used in cue reactivity research. Behavioral economic measures will assess product demand. A delay discounting task will assess preference for immediate reward,¹⁴⁸ while purchase tasks will be used to estimate level and elasticity of demand.¹⁴⁹⁻¹⁵¹ Sensory measures will be collected using the Duke Sensory Scale and Hedonic Attribute Scale. Drug effect measures include the Product Evaluation Scale and Drug Effects/Liking Scale.

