Cigarette tracking via EMA: For the field study, the key outcome is the total number of cigarettes smoked. Participants will be asked to complete REDCap questionnaires on their personal phone (iOS or Android). Participants can use the MyCap application to respond to questionnaires. Additionally, REDCap can interface with Twilio, a secure text-messaging platform, to send study related messages and surveys via SMS (text messaging). Proposed EMA methods are based on established best practices. Participants will complete 5 questionnaires every day. These questionnaires will occur at the same time each day: 11am, 1:30pm, 4pm, 6:30pm, and 9pm. These daily reports will be used to assess cigarette and e-cigarette consumption, and 10 items relating to subjective ratings of nicotine withdrawal (e.g., craving, irritability) and mood (e.g., calm/relax, happy). At 11am only, participants will complete selected items from the Hedonic Attribute Profile and Product Evaluation Scale. At 9pm only, participants will be asked to rate the taste, satisfaction,

Roswell Park Protocol Number: I 757820

enjoyment, and craving relief from the cigarettes they smoked that day. Participants will also be asked to take a CO measurement at this time. At the 1:30 and 6:30 prompts, participants will be asked about situational factors related to use (Location, smoking permitted, with others, activity, craving) and complete the Duke Sensory Evaluation scale. Participants also will be asked to take a picture of their research cigarette pack to ensure compliance. Surveys will be open for 1 hour after the scheduled time for completion. Appendix C demonstrates the EMA schedule and the questions asked at each daily report and pseudo-random prompt. Participants can earn up to \$10 for each day of EMA compliance, with compliance being defined as responding to ≥ 4 of 5 daily prompts (up to 14 days, totaling \$140). Studies that used similar methods had $>90\%$ compliance. [189, 190].

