This message:
Discourages me wanting to smoke
Makes smoking seem unpleasant to me
Makes me concerned about health effects of smoking

Negative Affect

How much did the label make you feel:
Anxious
Sad
Scared
Guilty
Disgusted

Roswell Park Protocol Number: I 757820

Thinking of Harms

How much did the labels make you think about:
The chemicals in the smoke of the cigarettes
Health problems caused by smoking
The harm your smoking might be doing to you
The harm your smoking might be doing to other people

Would you support or oppose a policy that required this label to appear on cigarette packages?
Strongly oppose – Strongly support

Would you support or oppose a policy that required this label to appear in advertising for cigarettes?
Strongly oppose – Strongly support

Remote Data Collection – EMA Schedule and Questionnaires

3 Daily Reports – 11 am, 4pm, 9pm (assessments < 5min)

How many cigarettes have you smoked since the last prompt?

How many of these cigarettes were research cigarettes?

How many of these cigarettes were not research cigarettes?

How you used any other tobacco products since the last prompt?

If yes: What product? How many times did you use it?

Please record your product weight with the provided scale.

RIGHT NOW: How would you rate your (0 – 100 VAS):

- Craving
- Irritability
- Anxiousness/nervousness
- Difficulty Concentrating
- Stress
- Bored
- Calm/Relaxed
- Happy
- Alert
- Enthusiastic

Provide Reminder to collect all cigarette butts in provided materials, store used pods

11 am Only (additional questions)

Hedonic Attribute Profile: In the past day, how would you rate the research cigarettes (1-7 Likert)

Draw

Irritation

Smoothness

Roswell Park Protocol Number: I 757820

Strength

Tobacco Taste

Similarity to Usual Brand

Product Evaluation Scale (1 - 7 Likert):

Was it satisfying?

Did it taste good?

Did it calm you down?

Did you enjoy the sensations in your mouth?

Did it reduce your craving for a cigarette?

Were there bothersome side effects?

Did you enjoy using the product?

Would you be willing to use the product long term?

Record CO measurement

9pm Only (additional questions):

Record CO measurement

Reflect on today as a whole: How would you rate your (0 – 100 VAS)

- Craving
- Irritability
- Anxiousness/nervousness
- Difficulty Concentrating
- Stress
- Bored
- Calm/Relaxed
- Happy
- Alert
- Enthusiastic

Thinking of the cigarettes you smoked today: How would you rate (0 – 100 VAS)

- Tastes like my own brand

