Please keep track of the amount of cigarettes and other tobacco you use. The scheduled prompts will ask you to report the number of cigarettes you've smoked. The random prompts will ask you to report on the situation in which you last used your product, such as the location and if smoking was allowed. We also ask that you store all used cigarette butts in the provided materials

Here are examples of the questions you will be asked at each assessment (show questionnaires). Do you have any questions?

We are also providing you with a CO monitor that will connect with your phone to take a CO measurement each night (demonstrate use).

We are also providing you with a scale to weigh other tobacco products that you may use, such as an e-cigarette or smokeless tobacco. If you use these other products, we would like you to weigh your product (e.g., pod, tank, dip tin) at the beginning and end of each day. If you are close to finishing your product and may start a new one, please weigh both the older and newer one at the beginning and end of the day.

Two additional times during the field study, we will ask you to videoconference with us as a study check-in and to have you respond to some questionnaires.

These are the cigarettes we are asking you to use during the field study (provide research cigarettes). Please use only these cigarettes and do not tamper with the cigarette pack. At random points in the study, we may ask you to take a picture of the cigarette pack.

Do you understand the procedures for the field study? Please call us if you have any questions.

Videoconferencing Sessions 2 & 3

Hello, today we are going to have you fill out a questionnaire. I will send it to you now. Have you been regularly storing your cigarette butts. Can I see how you are storing them?

Compliance: Your compliance has been great. Thank you!

Or: Your compliance has not met the standards. Please respond to more prompts or you may be discontinued for the study. Do you have any questions about the study procedures that may help you respond to more prompts?

Session 3 only:

Please pack up your supplies to prepare a return shipment. Can I see how you've stored your supplies in the box?

When we receive your materials, we will send you payment for completing the study. Thank you for participating.

Roswell Park Protocol Number: I 757820

Ads for the website/mobile app:

RESEARCH PARTICIPANTS NEEDED

Searching for:
21-69 year old daily cigarette smokers

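### No exhaled-CO reading precedes the research cigarettes, so change from usual-brand CO is lost and the arm comparison is less precise than it could be; the daily CO schedule also contradicts itself

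*Combined protocol and SAP*

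**What the plan says.** Section 3 names exhaled CO as a secondary endpoint, and Section 1.1 includes carbon monoxide exposure in the study aim.

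**When CO starts.** The schedule in Section 5.1 marks CO only in the column headed "Field (Daily for 14 days)", not at any of the three video sessions. The Session 1 description in 11.3 lists questionnaires and training, including usual-brand ratings on the subjective scales, but no CO reading. The baseline list in Appendix D has none either. Section 11.4 does place CO under its bullet for baseline measures and covariates, but what it describes there is the daily field collection. The monitor is already in hand at that point: "Session 1 will occur upon receipt of study materials by the participant", and Appendix D has staff demonstrate its use.

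**How often CO is taken.**
- Section 11.3, Remote Data Collection: "Participants will be prompted to measure their exhaled-air CO level and product weight twice each day using a personal monitor provided to them".
- Section 11.4, baseline bullet: "Exhaled air CO will be collected by the participants twice each day using a personal CO monitor provided by the researchers".
- Appendix C, EMA schedule: the item "Record CO measurement" appears under both the 11 am and the 9 pm additional questions.
- Section 11.4, EMA paragraph: after describing the 9 pm report, "Participants will also be asked to take a CO measurement at this time". No other time is named.
- Appendix D, training script: "We are also providing you with a CO monitor that will connect with your phone to take a CO measurement each night".

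**The concern.** CO is the only breath or body-fluid measure whose collection the protocol describes. Total nicotine equivalents and DNA adducts appear in Section 22.1, but no sample for them is scheduled. The other exposure-related measure, spent-filter analysis, is also confined to the field period.

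Every arm smokes a study cigarette, so the no-message arm controls for the message and not for the switch from the usual brand. With no reading before the switch, within-person change in CO is unavailable, and the arm comparison carries the full spread between smokers. That matters here because Section 1.2 predicts no significant effect on CO, and an imprecise comparison makes a non-significant result easier to obtain.

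The frequency conflict is a separate defect. It lies both within the protocol body and between the body and the script that staff read aloud. Following the evening-only text would cost morning readings, and following different texts would leave some participants with morning and evening values and others with evening values only.

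**Working it through.** The plan gives no SD, effect size, sample size or power for CO, so there is no stated CO figure to reproduce. The checks below use the plan's design figures and declared assumptions.

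**Inputs from the documents.** 14 field days (5.1); 240 completers and a pairwise alpha of 0.008 (22.1); four arms (11.3). Equal allocation is assumed, giving 240 / 4 = 60 per arm.

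**Step 1: readings at stake.**
- Twice daily: 14 × 2 = 28 per person, and 28 × 240 = 6,720 among completers.
- Once daily: 14 × 1 = 14 per person, and 14 × 240 = 3,360.
- Largest possible loss: 14 of 28, or 50%.

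**Step 2: what that loss does to a person's mean CO.** The variance of a mean of m readings is proportional to ICC + (1 − ICC)/m. The ICC is not in the documents and is taken as 0.2 to 0.8.
- ICC 0.2: 0.2 + 0.8/28 = 0.2286 and 0.2 + 0.8/14 = 0.2571. The ratio is 1.125, so the standard error is 6.1% wider.
- ICC 0.8: 0.8 + 0.2/28 = 0.8071 and 0.8 + 0.2/14 = 0.8143. The ratio is 1.009, so the standard error is 0.4% wider.

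**Step 3: detectable CO difference between two arms without a baseline.** In SD units, at 80% power, it is (z for two-sided alpha + z for power) × √(2/n).
- Alpha 0.008: (2.652 + 0.842) × √(2/60) = 3.494 × 0.1826 = 0.64 SD.
- Alpha 0.05: (1.960 + 0.842) × 0.1826 = 0.51 SD.

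**Step 4: the same with a baseline CO covariate.** Multiply by √(1 − r²), where r is the correlation of baseline CO with field CO. The documents give no r, so a range is shown at alpha 0.008.
- r = 0.5: 0.638 × 0.866 = 0.55 SD
- r = 0.7: 0.638 × 0.714 = 0.46 SD
- r = 0.8: 0.638 × 0.600 = 0.38 SD

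Step 4 compares against a model with no other covariates, so it shows the most a baseline with that correlation could add.

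**The case against.** A reader might infer that without a baseline the trial cannot see a rise in exposure at all. The documents do not support that. The design is randomized with a concurrent no-message control, so a message that raises CO would show as a higher level in that arm, without bias from the missing baseline. A trend across the field days is also estimable, and filter analysis gives separate information on mouth-level exposure. Only change from the usual brand is lost, and the stated aim concerns the effect of messages, not of switching cigarettes. Section 13.1, which likens side effects to those of participants' own cigarettes, is risk text that a CO reading would not settle. All of this stands.

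A reader might also infer that half the CO data will be lost. That is a ceiling. The 11 am form carries its own CO item, the forms run through one REDCap system for all sites, and just before the nightly line the script tells staff to show them: "Here are examples of the questions you will be asked at each assessment (show questionnaires)". Participants would have to skip an item on their screen, and Step 2 shows that even the full loss costs little precision. The shared forms also weaken the worry about differences between sites. The wording still conflicts and needs repair.

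On precision, the correlations are assumed and a single baseline reading is noisy. The plan already adjusts for sex and other tobacco use, and baseline cigarettes per day and nicotine dependence are collected and could be used too. The true gain would therefore be smaller than Step 4 suggests. This limits the benefit without removing it.

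**Conclusion.** The point holds as an inexpensive improvement to a secondary endpoint. No CO reading is planned before the research cigarettes start, so change from usual-brand CO cannot be estimated and cannot serve as a covariate. The between-arm contrast remains valid but less precise than it could be: about 0.64 SD detectable at alpha 0.008, against 0.55 to 0.38 SD with a baseline correlated at 0.5 to 0.8. Those figures assume equal allocation, 60 completers per arm and no other covariates.

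The CO schedule is internally inconsistent. The exposure is at most 14 of 28 readings per person, with a person-mean standard error 0.4% to 6.1% wider for an assumed ICC of 0.8 to 0.2. The more material loss would be the morning time point, and uneven time-of-day data if participants follow different instructions.

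**What to change.** 1. Record one supervised CO reading at Session 1, during the monitor demonstration, and add it to the Section 5.1 schedule, the Session 1 text in 11.3 and the Appendix D baseline list.
2. Because cigarettes and monitor arrive together before Session 1, tell participants when the kit is sent not to open a research pack until that reading is done.
3. Log the time since the last cigarette with the reading.
4. State in Section 22.1 that baseline CO is a covariate in the CO analysis.
5. Reconcile 11.3, both places in 11.4, Appendix C and Appendix D so that all give the same number and times of daily CO readings.

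The cost is about one minute at Session 1 with equipment already supplied, one added instruction, and wording changes. The drawback is that the baseline rests on one noisy value.

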 **ROSWELL**
PARK.
COMPREHENSIVE CANCER CENTER

SIGN UP

 **ARE YOU A CIGARETTE SMOKER?**
RESEARCH PARTICIPANTS NEEDED! **SIGN UP**

 **ROSWELL**
PARK.
COMPREHENSIVE CANCER CENTER

RESEARCH
PARTICIPANTS
NEEDED

Searching for **21-69 year old**
DAILY CIGARETTE SMOKERS **SIGN UP**
